11.2.2 Definitions

Evaluable for toxicity: All patients will be evaluable for toxicity from the time of their first treatment on study.

11.2.3 Disease Parameters

Patients with both measurable and un-measurable disease will be enrolled in the study. Treatment will continue until disease progression as defined above or unacceptable toxicity develops as determined by the treating physician.

12. DATA REPORTING / REGULATORY REQUIREMENTS

***** Please see Appendix F for Guidelines for Affiliate Institutions for Registration and Data Reporting Requirements.**

Adverse event lists, guidelines, and instructions for AE reporting can be found in Section 8 (Adverse Events: List and Reporting Requirements). The Data Safety Monitoring Plan is described in Section 12.3.

12.1 Data Collection

The Herbert Irving Comprehensive Cancer Center has an electronic clinical trials and data management system that will be used for data collection. CRFs for the study will be built into Velos for data entry. The system has full auditing capabilities which is web-based and housed on a server in a fully HIPAA compliant server room with restricted access and video camera monitoring. All users must login with their own application username and password. Users off campus must first access the Virtual Private Network with their assigned campus username and password and then use their application credentials. Users are only able to view study information if they are indicated as study personnel in our electronic IRB system, or an affiliate IRB system. Users are limited to access based on the role assigned in their corresponding protocol. Subject data is entered directly into the system, which (in the case of Columbia subjects) confirms the correct identity

of patients via an interface with the electronic medical patient index. Staff with the appropriate IRB defined roles can run reports within the system for reporting purposes.

12.2 Data Reporting

Responsibility for Data Submission

Case Report Forms will be completed for each subject enrolled into the clinical study through Velos eResearch. It is the investigator's responsibility for ensuring that all clinical and laboratory data entered on the corresponding CRFs are complete, accurate and authentic.

- Please refer to the tables provided in separate documentation regarding the case report form completion and source document submission requirements.

12.3 Data and Safety Monitoring Committee

The NCI-approved Data Safety and Monitoring Committee (DSMC) of the Herbert Irving Comprehensive Cancer Center (HICCC) will monitor every subject who receives treatment on this protocol for toxicity. This protocol will adhere to the policies of the currently approved HICCC Data and Safety Monitoring Plan (DSMP), which is in accordance with NCI and CUMC-IRB policy and guidelines. The committee is led by Dr. [name] and consists of HICCC faculty and staff with expertise in oncology, research pharmacy, research nursing, and data management. The DSMC convenes twice a month to review patient safety and the conduct of the trial. The PI will submit data and safety monitoring reports to the DSMC at a frequency to be determined by the DSMC based on risk to the subjects (*****DSMC forms will be provided separately *****).

At the time of renewal, the study team will submit the most recent DSMC approval letter for safety review to the CUMC IRB. Any modifications that are required by the DSMC to ensure patient safety will be submitted to the IRB. All protocol deviations, violations, and eligibility waivers will be submitted to and approved by the DSMC prior to being reported to the IRB. All study data reviewed and discussed during these meetings will be kept confidential.

The Coordinating Site will assure that there is a mechanism in place to distribute the report to all participating investigators for submission to their local IRB. The report will document that a review of data and outcomes across all centers took place on a given date. It will summarize the DSMC's review of the cumulative toxicities reported from all participating sites without specific disclosure by treatment arm. It will also inform site investigators of the study the DSMC's conclusion with respect to progress or need for modification of the protocol.

12.4 Quality Control and Quality Assurance

Independent monitoring of the clinical study for protocol and GCP compliance will be conducted periodically by the CPDM Compliance Core on behalf of the HICCC DSMC. Additionally, the Compliance Oversight Committee of the IRB at Columbia University Medical Center may audit the study at any time, per institutional policies and procedures.

The investigator-sponsor and Columbia University Medical Center will permit direct access of the study monitors and appropriate regulatory authorities to the study data and to the corresponding source data and documents to verify the accuracy of this data.

A risk-based approach will be used by the Compliance Core to determine the frequency, number of subject charts, and data elements to be monitored. The Compliance Coordinator will review the study status and summarize enrollment, toxicities, SAEs/UPs, dose escalation, statistical endpoints (e.g., stopping rules), etc. for the full DSMC membership at the regularly scheduled meetings.

Internal On-site Monitoring:

1. Initial, recurrent, and close-out on-site monitoring visits will also be conducted at remote clinical sites, as appropriate/feasible. Other sites will have monitoring performed remotely (see below for further details).
 - a. The study Monitoring Visit Log will be completed and signed by the monitor and the PI/CRNP/CRN and/or CRC and will be filed in the regulatory binder.
2. The Compliance Coordinator will communicate with the site coordinator/Site Principle Investigator to schedule the monitoring visit and arrange for access to study materials and documentation.
3. The assigned Compliance Coordinator will monitor IIT trials within 1 month after the first subject is enrolled and throughout the life of the study to ensure that the study is being conducted in accordance with the protocol, GCP, applicable federal and local regulations, and per all applicable SOPs. The Compliance Coordinator is responsible to notify the PI and CRNP/CRN/CRC of upcoming monitor visits and convey what information and documentation will be required for the visit(s). The Compliance Coordinator is responsible for verifying that informed consent is properly obtained, eligibility is met (via the central registration process), and all study procedures are conducted according to the study protocol. The Compliance Coordinator will also verify that the data reported in the CRF's accurately reflect source documents, that all toxicities have been reported to date, and that all SAE's/UPs/deviations/violations have been reported according to local IRB and HICCC DSMC requirements. The Compliance Coordinator will issue queries and ensure resolution in a timely and efficient manner. The Compliance Coordinator will also monitor for applicable regulatory compliance and research pharmacy compliance (if applicable) and communicate any deficiencies as appropriate.

12.5 Confidentiality

Information about study subjects will be kept confidential and managed according to the requirements of the Health Insurance Portability and Accountability Act (HIPAA). Those regulations require a signed subject authorization informing the subject of the following:

1. What protected health information (PHI) will be collected from subjects in this study
2. Who will have access to that information and why
3. Who will use or disclose that information
4. The rights of a research subject to revoke their authorization for use of their PHI

In the event that a subject revokes authorization to collect or use PHI, the investigator, by regulation, retains the ability to use all information collected prior to the revocation of subject authorization. For subjects who have revoked authorization to collect or use PHI, attempts should be made to obtain permission to collect at least vital status (i.e. that the subject is alive) at the end of their scheduled study period.

12.6 Source Documents

Source data is all information, original records of clinical findings, observations, or other activities in a clinical trial necessary for the reconstruction and evaluation of the trial. Source data are contained in source documents. Examples of these original documents, and data records include: hospital records, clinical and office charts, laboratory notes, memoranda, subjects' diaries or evaluation checklists, pharmacy dispensing records, recorded data from automated instruments, copies or transcriptions certified after verification as being accurate and complete, microfiches, photographic negatives, microfilm or magnetic media, x-rays, subject files, and records kept at the pharmacy, at the laboratories, and at medico-technical departments involved in the clinical trial.

12.7 Reporting to Novartis Pharmaceuticals Corporation

The primary site (CUMC) Principal Investigator will send complete Data transfers every six months during the course of the study to Novartis Pharmaceuticals Corporation. Novartis Pharmaceuticals Corporation may

request additional data transfers over the course of the study. The data will be provided in a readable format for all study participants. The data will not include any protected health information as defined under HIPAA.

Additionally, Novartis Pharmaceuticals Corporation will be provided monthly study status updates including a summary of:

- Recruitment (screened, enrolled, discontinued and on-going with dates and study drug dosing regimens)
- SAEs and safety reports to regulatory authorities
- Regulatory correspondence including IRB approval letters, IRB approved protocol, informed consent documents, and documents related to Novartis Pharmaceuticals Corporation.
- Investigational product Inventory
- Payment milestones.

12.8 Records Retention

Records relating to a specific research activity, including research records collected by investigators must be maintained for at least seven years after completion of the research (45 CFR 46.115(b); 21 CFR 56.115(b); 21 CFR 312.62). This was selected, as New York State (location of Sponsor) requires at least seven years for information. This retention period applies whether or not any subjects were enrolled in the study.

If the research is FDA regulated, records should be retained for at least two years after approval of the investigational agent by FDA; if it is not approved, records should be retained at least two years after the study is terminated and FDA is notified (note the additional requirement below for clinical research studies).

Clinical records, including consent forms that document clinical intervention or clinical diagnostic procedure research-related procedures, must be retained in medical records by the institution for at least seven years, per CUMC and NYP policy, which is based on state law.

Guidelines for Processing IND Safety Reports

The U.S. Food and Drug Administration (FDA) regulations require sponsors of clinical studies to notify the FDA and all participating investigators of any serious and unexpected adverse experiences that are possibly related to the investigational agent. The CUMC Principal Investigator will review all applicable IND Safety Reports and has the responsible for forwarding the IND Safety Reports to the Affiliate Institutions. The Affiliate Institution investigators are to review, send a copy to their IRB according to their local IRB's policies and procedures, and file a copy with their regulatory documents. All Affiliate site INDSR submissions, along with IRB acknowledgment (per local policies and procedures) are to be forwarded to CUMC for placement within the trial master file.

***** Please see Appendix F for Guidelines for Affiliate Institutions for Registration and Data Reporting Requirements.**

13. STATISTICAL CONSIDERATIONS

13.1 Study Design/Primary Endpoint (Sample Size: N=120 randomized evaluable patients)

This is a multi-center phase II, randomized, double-blinded, placebo-controlled trial to evaluate the efficacy of fulvestrant (or exemestane) with or without ribociclib in patients who have previously progressed on an aromatase inhibitor (preferably letrozole) plus CDK4/6 inhibitor (ribociclib or palbociclib or abemaciclib).

Primary Endpoint

The primary endpoint is progression free survival, defined as the time from randomization to the development of progressive disease or death.

Disease status will be assessed with comprehensive radiographic studies every three treatment cycles (approximately every 12 weeks (+/- 1 week), but the development of new signs or symptoms of disease in between scheduled evaluations may prompt off-schedule radiographic or non-radiographic evaluations. Disease status will be assessed based on RECIST 1.1 criteria for measurable (target) and non-measurable (non-target) disease, as outlined in detail in Section 11.

Secondary Endpoints:

All secondary endpoints, including overall response rate (complete response + partial response rates), clinical benefit rate (overall response rate + stable disease rate), overall survival, duration of response, adverse event rate, and biomarker assessment are exploratory in nature. In addition, patients registered under scenario #1 will be assessed for progression free survival, overall response rate, clinical benefit rate, and safety while receiving ribociclib with an aromatase inhibitor (pre-randomization). As there is no comparator arm for this pre-randomization part of the study, further statistical analyses on these will not be possible.

Response rates will be estimated as the proportion of enrolled patients who achieve response, as defined in Section 11. Patients who are lost to follow-up without a valid response assessment will be classified as non-responders.

Statistical analysis:

Progression-free survival will be estimated by Kaplan-Meier method and group differences between groups will be assessed using log-rank tests. Sensitivity analyses for PFS will be performed taking into consideration, but not limited to imputation of incomplete lesion measurements and study discontinuation due to progression/relapse, drug toxicity or death. Missing data patterns will be examined by summarizing the number of subjects randomized but not treated, the number of subjects who discontinued prematurely and the corresponding factors for early discontinuation. Given the potential the interval between two consecutive assessments may be longer in one arm, leading to an erroneous conclusion about differences between groups, we will perform an additional analysis (i.e. generalized log-rank) with interval censoring, especially if there is a difference in assessment schedules and considerable missing data.

Summary statistics will be calculated to describe the sample characteristics in each group. The distribution of patient responses (as defined by RECIST criteria) will be described using percentages % (n). Continuous outcomes will be summarized using mean \pm SD (standard deviation) or median (interquartile range) for non-normal data. Group comparisons will be evaluated using chi-squared or Fisher's Exact tests for categorical data and two-sided t-tests or ANOVA for continuous outcomes.

Analyses for of primary and secondary outcomes will be based on intention to treat principle, with the exception of safety endpoints, which will only be assessed in patients who receive at least one dose of treatment on study.

Subject to sample size limitations, subgroup analyses for subjects randomized to fulvestrant versus exemestane will also be considered.

All statistical analyses will be performed using SAS (version 9.4, SAS Institute Inc., Cary, North Carolina) with a type I error set at 0.05.

Sample Size Justification:

Assuming a median PFS of 3.8 months with fulvestrant alone upon progression⁸³, we predict that the addition of ribociclib to fulvestrant will lead to a median PFS of at least 6.5 months. Based upon the Evaluation of Faslodex versus Exemestane Clinical Trial (EFFECT), a randomized, double-blind, placebo-controlled, phase III trial of fulvestrant versus exemestane in patients who progressed on prior non-steroidal aromatase inhibition, the median time to progression was 3.7 months in each arm (HR=0.96, 95% CI 0.82

to 1.13, $p=0.65$). Thus, this new protocol amendment allows subject to be randomized to either fulvestrant or exemestane +/- ribociclib⁶⁹, without an impact on the study design and power. A one-sided log-rank test with an overall sample size of $N=120$ randomized and evaluable subjects and with the significance level alpha set at 2.5%, achieves 80% power to detect an effect size (difference in PFS) of 3 months. We will accrue approximately 150 patients to allow for a 20% drop-out rate, non-evaluable and non-randomized subjects.

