1.2 OBJECTIVES

1.2.1 Primary Objectives:

1. To evaluate the progression-free survival (PFS) of fulvestrant or exemestane with or without ribociclib after progression on anti-estrogen therapy plus cyclin-dependent kinase 4/6 inhibitor in patients with hormone receptor positive (HR+), HER2- breast cancer.

- **Endpoint: PFS.** Defined as the interval from time of randomization until objective disease progression (local assessment) or death from any cause. Kaplan-Meier estimates will be used to calculate medians and 95% confidence intervals for PFS. A one-sided log-rank test will be used to test for a difference in PFS between the two arms.

1.2.2 Secondary/Exploratory Objectives:

1. To assess the Overall Response Rate (ORR = complete + partial response rate) and Clinical Benefit Rate (CBR= ORR + stable disease rate at ≥ 24 weeks of follow up) in the study population in both arms of the trial, post-randomization.

- **Endpoints: ORR, CBR.** Evaluation of disease will be made according to RECIST criteria (version 1.1) in patients with measurable disease. As this study will enroll patients with measurable and un-measurable disease as defined by RECIST v1.1, ORR will only be assessed in evaluable patients. CBR will also be determined. Patients with non-measurable disease only can be categorized as ‘complete response’, ‘non-complete response’, ‘non-progressive disease’, or ‘progressive disease’, but are sometimes not evaluable. (Section 11.1.4.2: Evaluation of Non-Target Lesions).
 - **Duration of overall response:** The duration of overall response is measured as the time interval from when measurement criteria are met for complete or partial response (whichever is first recorded) until the first date that recurrent or progressive disease is objectively documented
2. For patients in registration scenario #1, to assess the PFS, ORR, CBR, and safety of ribociclib with an aromatase inhibitor in patients with metastatic or unresectable HR+ HER2- breast cancer. This analysis will be based on data collected in the pre-randomization component of the trial for patients registered under scenario #1. There is no comparator arm for this component of the trial, but it will add to the available clinical safety and efficacy data with ribociclib + AI in this population.

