Initial studies with lower dose fulvestrant 250 mg intramuscular monthly were disappointing, as they demonstrated minimal improvement over previously available anti-estrogen therapies. Two phase III non-inferiority trials compared fulvestrant 250 mg intramuscular once monthly with anastrozole 1 mg daily in a total of 851 post-menopausal patients who had previously progressed on anti-estrogen therapy, with the majority having previously received tamoxifen.^{65,66} (A previous study had established anastrozole as a modestly effective second line hormonal therapy compared to megestrol acetate in patients who had progressed on tamoxifen.⁶⁷) The time to progression on fulvestrant was 5.5 months vs. 4.1 months for anastrozole (HR=0.95; p=0.48) and the overall response rate was 19.2% vs. 16.5% (p=0.32), with a median duration of response of 16.7 mo vs. 13.7 mo. Subsequently, a phase III randomized trial compared fulvestrant 250 mg intramuscular once monthly to tamoxifen 20 mg daily as the initial anti-estrogen therapy in 587 postmenopausal patients with newly diagnosed or recurrent metastatic breast cancer.⁶⁸ In the 78% of patients who were ER-positive or PgR-positive, the two treatments were essentially equivalent in the first line setting, with an overall response rate of 31.6% vs. 33.9%.

The EFECT trial was a randomized phase III, double blind, placebo controlled trial comparing fulvestrant vs. the steroidal aromatase inhibitor exemestane 25 mg daily in 693 post-menopausal patients with ER or PgR-positive metastatic breast cancer who had disease progression on a non-steroidal aromatase inhibitor (anastrozole or letrozole)⁶⁹. Fulvestrant was administered with a loading dose of 500 mg intramuscular on day 0, followed by 250 mg doses on days 14 and 28, followed by 250 mg doses every four weeks. The median time to progression in both arms was equivalent (3.7 mo) and the overall response rate was 7.4% on fulvestrant vs. 6.7% on exemestane. (p=0.736). There was a trend towards more durable responses in patients who were treated with fulvestrant (13.5 mo vs. 9.8 mo).

More recent clinical studies have established that higher dose fulvestrant 500 mg intramuscular monthly is more effective than 250 mg and equally well tolerated and safe. Pre-surgical biomarker studies of fulvestrant indicate that PgR expression specifically is only decreased at higher doses of fulvestrant.⁷⁰⁻⁷² In the phase II

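### The primary PFS test adjusts for neither registration scenario nor endocrine backbone; a prespecified adjusted Cox model would cost little, gain modest power and supply the hazard ratio the plan lacks

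*Combined protocol and SAP*

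**What the plan says.** Section 1.2.1 sets the primary test: "A one-sided log-rank test will be used to test for a difference in PFS between the two arms". Section 13.1 (Statistical analysis) repeats it without strata or covariates: "group differences between groups will be assessed using log-rank tests". The planned summary of effect is also in Section 1.2.1: "Kaplan-Meier estimates will be used to calculate medians and 95% confidence intervals for PFS". No Cox model or hazard ratio is specified.

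The Synopsis and Section 6.1 describe allocation as 1:1 and name no stratification factors.

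The two factors appear elsewhere:
- **Registration scenario.** The Synopsis caps either scenario at 60% of accrual. Section 6.2 lists 27 patients treated under Scenario 1 before randomisation and says that scenario is closed.
- **Backbone.** The Synopsis and Sections 3.1 and 6.1 make prior fulvestrant lead to exemestane and prior exemestane lead to fulvestrant; otherwise the investigator chooses. Section 13.1 mentions a possible subgroup analysis by backbone.

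The Sample Size Justification says exemestane was added "without an impact on the study design and power". It cites a randomised fulvestrant-versus-exemestane trial with a median time to progression of 3.7 months in each arm and a hazard ratio of 0.96 (95% CI 0.82 to 1.13).

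**The concern.** If scenario or backbone is prognostic, a test that ignores it gives up power that adjustment recovers without more patients. Any unadjusted hazard ratio reported later would also lie closer to 1 than the adjusted one. With 120 patients and no stated stratification, chance imbalance would go uncorrected in the primary result.

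There are reasons in the protocol to think the factors could be prognostic.
- The cited 0.96 compares randomised drugs. Here backbone partly reflects treatment history, which that figure does not address.
- In the cited trial, Section 2.5 describes a 500 mg fulvestrant load "followed by 250 mg doses on days 14 and 28, followed by 250 mg doses every four weeks". This trial plans 500 mg throughout. Section 2.5 reports 500 mg against 250 mg at a PFS hazard ratio of 0.80. The no-impact statement therefore rests on a different regimen.
- Scenario 1 patients are selected before randomisation. Those who stop the lead-in for reasons other than progression, or cannot tolerate the lowest ribociclib dose, are not randomised (Sections 6.4 and 7.3), and prior fulvestrant is not allowed (Section 3.1).

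**Working it through.** **1. The plan's sample size.** The inputs in Section 13.1 are medians of 3.8 and 6.5 months, one-sided alpha 2.5%, power 80% and 1:1 allocation. Under exponential PFS, HR = 3.8/6.5 = 0.585.
- Schoenfeld: events = 4(1.960 + 0.842)²/(ln 0.585)² = 4 × 7.85/0.288 = 109.
- Freedman: events = (1.960 + 0.842)² × [(1 + HR)/(1 − HR)]², which rounds up to 115.
- With 24 months of accrual and 30 months of follow-up, about 119 of 120 patients have events. Power is 81.6% (Freedman) or 83.4% (Schoenfeld).
- Inflation: 120/(1 − 0.20) = 150.

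So N = 120 reproduces for 3.8 against 6.5 months. The stated 3-month difference (3.8 against 6.8, HR 0.559) would give about 87%, so 0.585 is used below.

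**2. Backbone effect from the protocol's figures.** Take 0.96 as fulvestrant relative to exemestane and 0.80 as 500 mg relative to 250 mg. Exemestane against 500 mg fulvestrant is then 1/(0.96 × 0.80) = 1.30. Taking the two drugs in the cited trial as equal gives 1/0.80 = 1.25. Populations and loading doses differ, so this is only indicative. The documents give no figure for scenario.

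**3. Power.** Simulated trials had 120 patients, true HR 0.585 and one-sided 2.5%. Monte Carlo error is about 0.6 to 0.8 points. The table shows unadjusted → adjusted Cox power (%).
- Setting A: 27 patients in Scenario 1, 20% on exemestane, 24-month accrual, 12 months of follow-up.
- Setting B: 22 patients in Scenario 1, 30% on exemestane.
- Setting C: 27 patients in Scenario 1, 50% on exemestane, every patient with an event.

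| Prognostic HR, scenario / backbone | A | B | C |
|---|---|---|---|
| none | 80.9 → 80.6 | 82.1 → 82.3 | 80.6 → 79.7 |
| 1.5 / 1.5 | 77.7 → 80.4 | 79.1 → 81.6 | 77.5 → 81.1 |
| 2.0 / 2.0 | 72.4 → 79.3 | 73.7 → 81.5 | 70.9 → 81.2 |

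- Setting A with 30 months of follow-up: 81.3 → 81.0, 79.0 → 81.7 and 75.1 → 81.1 for the same three rows.
- Backbone only, HR 0.96 (Setting A): 80.6 → 80.0.
- Backbone only, HR 1.3: 81.2 → 82.0 in Setting B. With 12 months of follow-up, 79.4 → 79.4 (20% exemestane) and 79.5 → 80.2 (50%). With 30 months, 80.7 → 80.6 (20%) and 79.8 → 81.0 (50%).
- Unadjusted HR in Setting A: 0.578, 0.591 and 0.608 down the rows. The adjusted HR stayed at about 0.575.
- Log-rank with four strata (scenario by backbone), Setting A: 78.4, 77.3 and 77.2%. With no prognostic effect it loses 80.9 − 78.4 = 2.5 points.

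**4. Validity.** With no treatment effect, one-sided rejection over four runs was 2.4 to 3.1% unadjusted and 2.6 to 2.9% adjusted. There is no consistent inflation from omitting the factors.

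**5. Chance imbalance.** With 27 of 120 in Scenario 1 and 60 per arm, the number falling in one arm has SD √(27 × 0.25 × 93/119) = 2.3. The between-arm difference in share has SD 2 × 2.3/60 = 7.7 points, so about ±15 points covers 95% of allocations. If the scenario HR were 1.5, a 15-point imbalance would shift the log HR by roughly 0.15 × ln 1.5 = 0.061, a factor of 1.06. An HR of 0.585 could then appear as about 0.55 or 0.62.

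**The case against.** The strongest reply is that, at the documents' own figures, the effect is negligible. The quoted 0.96 implies no loss, and the chained 1.3 implies a gain of −0.1 to 1.2 points. A 10-point gain needs both factors at 2.0 and an even backbone split, which nothing in the protocol supports. This stands, and it sets the scale of the point.

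Other limits also stand:
- The 27 Scenario 1 patients were treated before randomisation, and Section 6.4 expects some to leave first, so 27 is a ceiling (27/120 = 22.5%).
- A reader might infer that both factors are already recorded before allocation. Scenario is fixed by then. For discretionary backbone choices the protocol does not say when the choice is recorded.
- A reader might take prior chemotherapy as distinguishing the scenarios. Exclusion criterion 4 allows one prior regimen in both.
- On-treatment Scenario 2 patients were unblinded at the end of August 2023 (Sections 10.3 and 13.6). Changing the primary analysis after that carries a credibility cost.

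None of these removes the case for adjustment. The possible loss is about 1 point and the possible gain is larger. The model also supplies an effect estimate that the plan does not define.

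**Conclusion.** The point holds as an efficiency and chance-imbalance issue of modest size. Adjustment gains about 0 to 1 power point at the protocol's own backbone figures, about 3 points (2.5 to 3.6) if both factors have a hazard ratio of 1.5, and 6 to 10 points only in the extreme case of 2.0 for both. It costs up to about 1 point if neither is prognostic. These sizes rest on assumed prognostic strengths, an assumed backbone split, exponential PFS and at most 27 Scenario 1 patients.

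Two stronger readings are tempting and not supported. The first is that the primary test is biased or invalid: its type I error is sound. The second is that the plan's hazard ratio is attenuated: the plan specifies none, so this would apply only to an unadjusted hazard ratio added later. Separately, the statement that exemestane leaves power unaffected is not established by the trial cited for it, though the likely consequence is small.

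**What to change.** 1. Check that the backbone intended at randomisation was recorded before allocation. If it was not, adjust for scenario and for the prior therapy that dictates the backbone.
2. In Section 13.1, prespecify a Cox model for treatment arm with main effects for registration scenario and intended backbone, reporting the adjusted hazard ratio and 95% CI. Keep the unadjusted log-rank alongside it.
3. Make the adjusted model primary only if it is signed off before anyone reviews comparative PFS data, and record who had access to treatment codes after the August 2023 unblinding. Otherwise keep the log-rank as primary and make the adjusted model the key supportive analysis.
4. Do not substitute a log-rank with four strata: it loses about 2 to 3 points if the factors are not prognostic.
5. Qualify the no-impact statement in the Sample Size Justification by noting the different fulvestrant regimen in the cited trial.

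The cost is an amendment to the analysis text, a check on when backbone was recorded, up to about 1 power point if neither factor matters, and the need to justify a change made after the 2023 unblinding. No extra patients or visits are needed.
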